**D5.6 Sharing Data:**

If the subject agrees, the data collected and generated from this study will be shared to the Registry for Stroke Recovery (RESTORE-Pro#00037803) by the subject's registry ID. Sharing data from this study with the registry will allow for more targeted recruitment efforts in the future and allow researchers at MUSC to have a more complete registry with key stroke recovery elements including common data and physical function characteristics that are applicable to multiple studies. MUSC researchers and collaborating facilities will be able to query data sets to learn more about recovery of subjects after their stroke through institutionally managed secure servers that will assure HIPAA privacy and security compliance.

**Appendix:****1. Total enrollment table**

Please refer to statistical analytic plan for sample size calculation, 36 subjects (18 subjects for part I and another 18 subjects for part II) are needed.

TARGETED/PLANNED ENROLLMENT: Number of Subjects			
Ethnic Category	Sex/Gender		
	Females	Males	Total
Hispanic or Latino	2	2	4
Not Hispanic or Latino	16	16	32
Ethnic Category: Total of All Subjects*	36		
Racial Categories			
American Indian/Alaska Native	1	1	2
Asian	1	1	2
Native Hawaiian or Other Pacific Islander	0	0	0
Black or African American	8	8	16
White	8	8	16
Racial Categories: Total of All Subjects*	18	18	36

**2) Protection to Human Subjects:****Potential Risk to Human Subjects**

**tDCS:** Extensive animal and human evidence and theoretical knowledge indicate that the presently used tDCS protocols up to 2mA are safe. It involves minimal risk to human subjects. Commonly reported side effects are as followed: skin irritation with itching, tingling, burning sensation, transient headache or nausea. For part one of the study where the level of current is being tested higher than 2mA, there maybe potential side effects. They include burns under the pads, seizure, changes on MRI, and changes in blood test results. If patient experience any of serious adverse event which meet the 'stopping rule", the trial will be evaluated by DSMB and make further decision. The risks associated with pregnancy and tDCS are unknown. Pregnant women are excluded. All female subjects that are of childbearing age that have not had a hysterectomy will be ask their method of birth control and will be questioned prior to each session if there is a possibility that they might be pregnant. Acceptable forms of include birth control condom use or hormonal contraceptives.

**MRI:** The test will be done using equipment similar to that used for clinical MRI. The current revision of the US Food and Drug Administration guidelines (U.S. Department of Health and Human Services, Food and Drug Administration, Center for Devices and Radiological Health, Guidance for the submission of premarket

notifications for magnetic resonance diagnostic devices, Washington, DC. November 14, 1998) applies to this study. These guidelines state that magnetic resonance imaging systems with main static magnetic field strengths of 4.0T (a measure of magnetic strength) and less, such as the ones used for this study, can qualify as non-significant risk devices.

Because the MRI machine acts like a large magnet, it could move iron-containing objects in the MRI room during your examination, which could in the process possibly harm you. Precautions have been taken to prevent such an event from happening; loose metal objects, like key chains, are not allowed in the MRI room. If you have a piece of metal in your body, such as a fragment in your eye, aneurysm clips, ear implants, spinal nerve stimulators, or a pacemaker, you will not be allowed into the MRI room and cannot have a MRI. Having a MRI may mean some added discomfort to you. In particular, you may be bothered by feelings of claustrophobia and by the loud banging noise during the study. Temporary hearing loss has been reported from the loud noise. This is why you will be asked to wear earplugs. At times during the test, you may be asked not to swallow for a while, which can be uncomfortable.

**Venipuncture:** The risks of drawing blood include temporary discomfort from the needle stick, bruising and infection. Fainting could occur. There will be a total of 30 ml's collected for the 3 blood draws (10 ml's per draw).

**TMS:** The TMS coil makes noise, much like a loud pop when it produces its magnetic energy. You may or may not feel your thumb twitch depending on the strength of the TMS pulse, but you might also feel your facial muscles twitch slightly just around your eye. This twitch is just as brief as the thumb twitch and is a result of the TMS directly stimulating the facial nerves and muscles that run directly under your scalp. It is not painful. TMS can cause heating or movement of metallic objects in or near the head. In addition, the inactivation of pacemakers, medication pumps, cochlear prostheses and other implantable hardware may occur. Magnetic media such as credit cards, etc. and watches near the coil may also be damaged. To minimize this risk the researchers will have asked you about any metal implants which would exclude you from the study. There is a known risk of inducing a seizure during rTMS, however, it is not used in grant proposal.

**Motor assessments:** Motor assessments may occasionally cause fatigue; however you have the option to adjust your pace as needed to complete the test.

### **Protection to Human Subjects:**

#### **tDCS:**

- 1) Strictly follow the inclusion and exclusion criterias
- 2) Study part 1 is a tolerabilty study. Adverse events are recorded carefully on every visit on every patients, if major response occurs, DSMB will be notified immediately.

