#### Aim 1: To determine the optimal current in stroke patients

##### D1.1 Design:

This aim is a phase I type study to determine the most efficacious current for tDCS, recognizing that this current level must be tolerable and safe. The trial design is adapted from the classical, gold-standard 3+3 drug trial design, which is commonly used to find the maximal tolerable dose for a chemical drug. The main justification for this design is that the maximal tolerable current (dose) is usually and arbitrarily defined as the dose at which one-third of the patients experience current (dose)-limiting major side effects/response. The algorithm for current (dose) escalation is detailed in (**Figure 4**). The study starts with 1 mA : (a) if no major response occurs in any of the three subjects, a next current at 2 mA will be used next; (b) if major response occurs in 2-3 study subjects, then the trial will stop at this current level; (c) if major response occurs in one subject, then 3 additional study subjects will be entered to further test the safety of same current dose; if no major response occurs, then the current will be escalated next current level; if further major response occurs, then the trial will terminate. The previous current level will be defined as the maximal tolerable current (dose). The current tDCS device available on the market (Chattanooga Dual-Channel Iontophoresis Device) for research use has a maximal current of 4.0 mA. The sequence for current escalation will be 1.0 mA >> 2.0 mA >> 2.5 mA >> 3.0 mA >> 3.5 mA >> 4.0 mA.

While we vary current in this protocol, other features of the stimulation will be controlled:

- **Duration of stimulation will be 30 minutes:** Data show the increased excitability of tDCS can last as long as 90 minutes. Our rehabilitation intervention will take one hour. Thus, by using 30 minutes of

stimulation, as has been commonly used in stroke studies, we should ensure that the potentially beneficial effects of the stimulation will not wear off during the course of rehabilitation.

- **Size of electrode will be 3 × 5 cm^2:** The commonly used 3 × 5 cm^2 size pad is chosen because it is adequate to cover the the primary motor cortex – our area of interest for brain stimulation in stroke subjects to facilitate upper extremity motor function recovery.

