### **Definition of Major Response and “Stopping Rule”:**

A major response is defined by any of the following serious adverse events occurring during the study period. It serves as the “stopping rule” as detailed in the **Figure 4** above.

- Second degree scalp burn at the site of electrode pad; or
- Seizure; or
- New lesion(s) on DWI sequence of MRI scan and the lesion(s) is not explained by any other cause(s) or decreased ADC under the electrode stimulating motor cortex area; or
- Patient discontinues from the study due to any reasons above.

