25. Note that these analyses must be completed for each set of 3 subjects in a group to determine whether one or more major responses occurred before enrollment continues. If no major response occurs, the next 3 subjects will be entered to go through procedure 9-23 according to **Figure 4**.

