### **D1. 4. Anticipated Results:**

We anticipate that 4.0 mA will be tolerable and safe both at clinical and subclinical levels, as evidenced by a lack of major responses in the study subjects. In addition we expect that 4.0 mA will produce the largest increase in MEPs amplitude compared with other current levels.

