#### **D4. 1 List of Protocols:**

##### **MRI Protocol:**

Study subjects will be scanned at the Center of Advanced Imaging (**NI core**) by a Siemens 3T Trio MRI scanner using a standard radiofrequency head coil at before and within 2 hours after stimulation. During MRI, electrode positions will be marked by placing vitamin pills detectable in MRI scans at the center of the tDCS electrodes. Areas of 3\* 5 cm, which were the size of the tDCS electrodes, will be determined as regions of interest (ROI) around this center for the stimulated primary motor cortex. Head motion will be minimized by foam padding and forehead-restraining straps if necessary. T1 contrast enhanced weighted anatomical\_image (IR/TR/TE = 1100/1900/3.37; resolution = 1 x 1 x 1 mm^3; FOV = 256 x 256), Fluid attenuated inversion recovery (FLAIR, TR/TE = 9000/89; resolution = 0.43 x 0.43 x 5 mm^3; FOV = 220 x 192.5) and DWI (TR/TE = 5.5 s/99 ms; resolution = 3 x 3 x 3 mm^3; FOV = 222 x 222). In T1- diffusion-weighted studies, and ADC maps will be visually inspected for signal changes by a blinded board certified neuro-radiologist or neurologist. Furthermore, pixel by-pixel subtraction of the post-stimulation ADC parametric images from the baseline ADC parametric images will be performed by means of an implemented scanner software algorithm for improved differentiation and highlighting of possible locally restricted ADC changes. Statistical difference between the ADC values before and after stimulation will be calculated and analyzed.

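### Part 1's escalation rule and prompt DSMB triggers respond only to the listed major responses, so any other serious adverse event neither requires prompt DSMB notice nor holds the next current

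*Combined protocol and SAP*

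**What the plan says.** The section defining the major response and stopping rule opens: "A major response is defined by any of the following serious adverse events occurring during the study period". Four items follow: a second-degree scalp burn at the pad; a seizure; a new DWI lesion without another explanation, or decreased ADC under the electrode; and "Patient discontinues from the study due to any reasons above". The fourth points back to the first three, so it is not a catch-all.

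The rules that act on safety in Part 1 all use this list:

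- **Escalation (D1.1):** "if no major response occurs in any of the three subjects, a next current at 2 mA will be used next". One major response adds three subjects; two or three stop the trial at that level.
- **Between-cohort check (D1.2, step 25):** "If no major response occurs, the next 3 subjects will be entered".
- **Immediate DSMB notice (Protection to Human Subjects, tDCS, item 2):** "Adverse events are recorded carefully on every visit on every patients, if major response occurs, DSMB will be notified immediately".
- **DSMB evaluation (Potential Risk to Human Subjects, tDCS):** for a serious adverse event that meets the stopping rule.
- **Early stop (Data Safety Monitor Board section):** two or more major responses at one current level. The sentence about meeting sooner than six months follows directly and names no other trigger.

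Otherwise the DSMB meets every six months, with a general safety remit.

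**The concern.** The protocol recognises serious adverse events as a wider class than major responses, since it speaks of those that are listed or that meet the rule. For the remainder, the text provided requires recording but sets no prompt route to the DSMB and no pause. If a subject at 2.5 mA died, had a cardiac event, or worsened neurologically without a qualifying DWI or ADC change, the cohort would still count as free of major responses, and step 25 would enter the next three subjects at 3.0 mA.

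Scheduled imaging does not close the gap. Scans are done "using a standard radiofrequency head coil at before and within 2 hours after stimulation", and the Day 14 visit in Table 2 has no MRI. A neurological event after that scan counts only if it is a seizure or if an unscheduled scan shows a qualifying change.

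At stake is the safety of stroke subjects taken above 2 mA, the range Part 1 was set up to explore. A higher current could open after a possibly related serious event that the DSMB has not seen.

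**Working it through.** **The plan's own counts.** D1.1 lists six currents (1, 2, 2.5, 3, 3.5 and 4 mA). Stopping in the first cohort gives 3 subjects. No major response gives 6 × 3 = 18. Expanding every level gives 6 × 6 = 36. These match the 3, 18 and 36 in D1.3, so the 3+3 rule has been read as intended. Figure 4 is not shown, but D1.1 states its algorithm in words.

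**The wording.** Take a cohort with no listed event and one unlisted serious adverse event. D1.1 counts zero major responses and escalates. Step 25 enters the next three subjects. The immediate-notice, evaluation and early-stop conditions are all unmet. This holds whatever the rate of unlisted events, because that rate enters none of the rules.

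**Illustration of exposure before the next scheduled meeting.** Inputs from the documents: 2 to 3 subjects per month (D5.1), follow-up at Day 14 (Table 2), three currents above 2.5 mA with three subjects each (at most 9), and six-monthly DSMB meetings. Assumptions:

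- The event occurs at time 0 in subject k (1, 2 or 3) of the 2.5 mA cohort.
- Subjects are spaced s = 1/2 or 1/3 month apart.
- After each cohort's last stimulation there is a hold h of 14 days (0.46 month; follow-up only, no analysis time), 28 days (0.92) or 42 days (1.38).
- No listed major response occurs, and nobody reports the event voluntarily.

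Subject j of later cohort c (c = 1, 2, 3 for 3.0, 3.5 and 4.0 mA) is stimulated at

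T = (3 − k)s + c·h + (3(c − 1) + j)s months.

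Example with k = 1, s = 0.5, h = 0.46: the first 4.0 mA subject has T = 1.0 + 1.38 + 3.5 = 5.88, within six months. The second has T = 6.38, outside it. The count is 3 + 3 + 1 = 7.

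The worst case counts T ≤ 6 (event just after a meeting). The average treats the wait to the next meeting as uniform over 0 to 6 months, sums max(0, 1 − T/6) over the nine later subjects, and averages over k. Aim 1 length is 18s + 6h.

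| Hold | Per month | Worst case, k = 1, 2, 3 | Average | Aim 1 length (months) |
|---|---|---|---|---|
| 14 d | 2 | 7, 8, 9 | 3.2 | 11.8 |
| 14 d | 3 | 9, 9, 9 | 4.6 | 8.8 |
| 28 d | 2 | 6, 6, 6 | 2.4 | 14.5 |
| 28 d | 3 | 7, 8, 9 | 3.3 | 11.5 |
| 42 d | 2 | 4, 5, 6 | 1.8 | 17.3 |
| 42 d | 3 | 6, 6, 6 | 2.4 | 14.3 |

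Three of the six rows exceed the one year planned for Aim 1: 28 days at 2 per month, and both 42-day rows. The three that fit give 7 to 9 in the worst case and 3.2 to 4.6 on average. In all 18 worst cases the count is at least 4, so 3.5 mA has opened.

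**The case against.** The strongest reply is that this is a research plan, not a safety-reporting manual. Institutional review board policy, or a monitoring plan not provided, may already require expedited reporting. A reader might infer that unlisted events would go unreported; the documents do not support that, and those duties cannot be judged here. Reporting elsewhere would not, however, by itself put a hold into D1.1 or step 25.

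Second, a 3+3 design needs a prespecified list. The risks section names burns, seizure, MRI changes and blood-test changes above 2 mA. The first three correspond to listed items, and D1.3 says the biomarkers were dropped as a stopping rule on DSMB advice. The examples given here are not named as expected risks. This stands as a defence of the list, which need not change. It does not explain why notice to the DSMB should be equally narrow.

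Third, other channels exist: the investigator administers every stimulation, subjects are told to call about untoward effects, there is a Day 14 visit, and the DSMB helps with problems the investigator reports. A sensible investigator would probably pause. None of these, though, is a required prompt trigger or hold.

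Fourth, it is tempting to say the plan would declare 4.0 mA "tolerable and safe both at clinical and subclinical levels, as evidenced by a lack of major responses in the study subjects" despite such an event. That sentence is a forecast under Anticipated Results, not a decision rule. Nor is it shown that unlisted events would be left out of the analysis: D1.3 already summarises the safety measures by current.

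Finally, the exposure counts are conditional and driven by assumptions. That is correct, and the point does not rest on them.

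**Conclusion.** The point holds on the text provided and should be fixed. The written rule admits three more subjects at a higher current after an unlisted, possibly related serious adverse event, with no required prompt DSMB notice. Review is otherwise left to the six-monthly meeting. This follows from the wording and needs no event rate; none is given, and no probability of harm is claimed.

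The illustrative size, for one event at 2.5 mA, is about 4 to 9 later subjects in the worst case and about 2 to 5 on average. It assumes silence until the scheduled meeting, no listed major response, and the accrual and hold times above, some of which overrun the planned year. It should not be read as a forecast.

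**What to change.** - **Notice.** In the tDCS paragraphs of Potential Risk to Human Subjects and Protection to Human Subjects, require immediate DSMB notification of any serious adverse event in Part 1, listed or not.
- **Hold.** In D1.1 and D1.2 step 25, add that after an unlisted serious event that is possibly related to stimulation or unexplained, the next current does not open until the DSMB or its chair has reviewed it. Clearly unrelated events need notice only, consistent with the attribution wording already used for DWI lesions.
- **Optional clarification.** In D1.3, state that the safety summary by current includes all serious adverse events.

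The major-response list, 3+3 counts, visits, procedures and sample size stay unchanged. The cost is a short amendment, a few extra notices to a three-member board, and possibly a short pause before escalation.

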#### **MRI:**

- 1) MRI screening form will be done at the time of recruitment, and patient will be excluded from study if he/she has contraindication for MRI or can not tolerate the MRI scanner
- 2) Headphone or earplug is provided to the study patient to minimize the noise from magnetic field.

#### **TMS:**

- 1) strictly follows the published guideline about TMS application. TMS is only applied by skilled and well trained staff in the center of brain stimulation.
- 2) rTMS will not be used in our grant application which has a risk of seizure.
- 3) Conduct a daily assessment after each study session to collect more information about side effect

**Potential Benefit of the study:**

There will be no other direct benefit to you from participating in this study except the one hour rehabilitation therapy; however, it is hoped that the information gained from the study will help in the treatment of future stroke patients with conditions like yours, and help the researchers to develop new rehabilitation treatment for stroke survivors in the future.

**Data Safety Monitor Board and Data safety monitoring plan:**

The DSMB will be composed of three of external members who are not involved with the study design or experiments: [name](Chair of DSMB, MD, board certified neurologist, ex-IRB committee member), [name] (DSMB member, DO and board certified Neurologist) and [name] (DSMB member, PhD biostatistician).

The DSMB member will meet every 6 months. If 2 or more major responses that occurs in the study part 1 at specific current level, the study need to be stopped early. The DSMB will meet earlier than 6 months interval.

The chair will lead the meeting with two members, Specifically they will

- 1) protect the safety of the study participants;
- 2) review the research protocol, informed consent documents, amendments, and plans for data safety and monitoring;
- 3) evaluate the progress of the trial, including periodic assessments of data quality and timeliness, recruitment, accrual and retention, participant risk versus benefit, performance of the trial sites, and other factors that may potentially affect study outcome;
- 4) review study performance, make recommendations and assist in the resolution of problems reported by the Principal Investigator;
- 5) report to IRB on the safety and progress of the trial;
- 6) ensure the confidentiality of the study data and the results of monitoring
- 7) advise the IRB and the study investigators as to whether the protocol should continue as scheduled or undergo a modification due to a finding from the monitoring process

